**A Trial of “Opening Doors to Recovery” for Persons with Serious Mental Illnesses**

**ClinicalTrials.gov: Identifier NCT04612777**

**09/13/2022**

**Revised 07/24/2024**

## Methods

### Participants

Enrollment will begin in December 2014 and continue until the target sample size is achieved, which is expected to take approximately three years. Adults with serious mental illnesses (SMI) will be recruited from three inpatient facilities: a state psychiatric hospital in Savannah, Georgia; a crisis stabilization unit (CSU) in Savannah; and a CSU in Brunswick, Georgia.

Eligibility criteria will include: (1) 18–65 years of age; (2) English speaking; (3) diagnosis of a psychotic or mood disorder (confirmed with the *Structured Clinical Interview for DSM-5 Disorders* (SCID-5); (4) two separate inpatient admissions, each for  $\geq 2$  days, in the past 12 months; (5) absence of intellectual disability or dementia; (6) capacity to provide informed consent; (7) being discharged to reside within one of seven counties with case management (CM) services provided by the public mental health agency hosting the research; (8) not currently receiving assertive community treatment (ACT) or CM; and (9) eligible to receive CM; i.e., unable to complete daily living activities in at least two areas, despite caregiver or behavioral health staff support, and requires assistance in one or more areas of managing their illness.

### Interventions

*Opening Doors to Recovery* (ODR). The Community Navigation Specialist (CNS) team's process of community navigation is a broader function than traditional CM as it includes mapping and connecting clients to all available local resources, which requires being embedded in the community. The CNSs benefits from commitments of diverse collaborative ODR partners (who convene as part of a "Blue Ribbon Taskforce"), including local treatment providers, law enforcement, employers, and housing programs. Those enrolled in ODR consent to information sharing that allow the CNSs to overcome communication barriers in pursuit of their clients' recovery goals. One example of this is a novel Police–CNS Linkage System that allows law enforcement officers to talk directly to a CNS in the event of a police encounter—a component of ODR also being studied separately. The CNS team's caseload will be capped at 40. Each CNS is expected to meet with the client at home or in community settings at least monthly, with the client having contact with at least one CNS weekly.

*Case Management* (CM). For the control group, we considered both traditional CM and intensive case management (ICM) to be different enough from ODR for the purposes of testing hypotheses. Because we are limited to what is available locally for the control group, patients will receive CM if being discharged to reside in six of the counties, and they will receive ICM if living in Chatham County, the most urban/populous county, which offers ICM services. CM services, as defined by the State mental health agency, focus on assisting the individual with: developing natural supports to promote community integration, identifying service needs, linking to services/resources, and coordinating services to maximize integration and minimize service gaps. Outcome expectations include decreased hospitalizations and incarcerations, as well as increased housing stability, job-related activities, community engagement, and recovery. CM is provided by a licensed practitioner, whose caseload does not exceed 50. Contact must be made with the individual  $\geq 2$  times per month, at least one of which must be in-person, in a non-clinic setting. ICM is very similar, but four in-person visits are required monthly, at least 60% of total contacts must be face-to-face, and at least 50% must be delivered in non-clinic/community-based settings. An ICM team includes nine professionals, and the team's maximum case load is 200 (22 per team member).

### Referral, Assessment, and Randomization

All procedures will be reviewed and approved by the university's and the State's Institutional Review Boards. Clinicians at the three sites will refer potentially eligible patients who will then be evaluated for their interest in taking part in the study and capacity to give informed consent. Trained research assessors will complete the initial/baseline assessment

within about a week before discharge. After eligibility screening, consent, and the assessment, the patient will be randomized at a 1:1 ratio to ODR or CM using a computer-generated algorithm. The study statistician will create the randomization list, by randomly alternating blocks of 2 or 4, and the resulting sequential treatment assignments will be sealed in opaque envelopes. After the patient is found to meet eligibility criteria, gives informed consent, and completes the baseline assessment, the research assessor will open the next envelope in the sequence and inform the ODR or CM provider of the treatment assignment.

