### **Data Analyses**

Between-group comparisons will rely on intention-to-treat analyses. Analyses involving hospitalizations and arrests will be performed using both binomial and Poisson generalized linear models for binary outcomes and counts, respectively. Analyses of change in housing and recovery measures will be performed using linear mixed models on all available data at each timepoint. Time in months will be used as a continuous predictor (growth curves) with measures at baseline, 4-, 8-, and 12-months. For the primary outcome analysis (12-month endpoint) the model structure will include group (ODR vs. CM), time, and group-by-time interactions, with a random intercept for subject. For those measures that indicate significant 2-group differences, we will compare ODR against ICM specifically, to further define effects (post-hoc analyses). For count/duration of hospitalizations and number of arrests, we will do conditional tests (comparing only those with non-zero values) to reduce the effects of zero inflation and get meaningful effect sizes across groups.

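### County fixes the control service, but neither the randomization nor the hospitalization and arrest models use it: a modest loss of precision, not bias

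*Combined protocol and SAP*

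**What the plan says.** All places are in the combined protocol and SAP, under Methods.

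- **Allocation** (Referral, Assessment, and Randomization): "the patient will be randomized at a 1:1 ratio to ODR or CM using a computer-generated algorithm". On the list: "The study statistician will create the randomization list, by randomly alternating blocks of 2 or 4". At assignment, "the research assessor will open the next envelope in the sequence". One sequence is described, with no stratification by county or referral facility.
- **County is a baseline fact** (Participants, criterion 7): eligibility requires "being discharged to reside within one of seven counties with case management (CM) services". County must therefore be known before randomization. Referral facility (three sites) is known too.
- **County sets the control service** (Interventions, Case Management): "patients will receive CM if being discharged to reside in six of the counties, and they will receive ICM if living in Chatham County". Chatham is also singled out as the most urban and populous county.
- **Models** (Data Analyses): hospitalizations and arrests are "performed using both binomial and Poisson generalized linear models for binary outcomes and counts, respectively", with no covariates listed. For the longitudinal measures, "the model structure will include group (ODR vs. CM), time, and group-by-time interactions", plus a random intercept per subject.
- **CM versus ICM** appears in the analysis only as a post hoc comparison of ODR with ICM, for measures that already show a significant difference.

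No target sample size, Chatham share or event rate is stated.

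**The concern.** Blocking the overall sequence keeps the arm totals close. It does nothing to keep the arms alike in county. If the arms differ by chance in their Chatham share, two things follow.

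First, any difference in readmission or arrest risk between Chatham and the other six counties enters the ODR versus control contrast, and no planned model removes it. Second, the share of controls who receive ICM equals the share of controls who live in Chatham, so the make-up of the comparator is also left to chance.

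The plan itself marks county as a divide in both service and urbanicity. Location may also affect how completely hospitalizations are recorded: Outcome Data Collection says the State agency held CSU data only from January 2017, and that the two referral CSUs supply their own data for the full period. That location predicts the outcomes is an inference, because the documents report no risk by county.

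**Working it through.** The plan gives no figure to reproduce. Taken from the documents: 1:1 allocation, blocks of 2 or 4, no strata, and seven counties of which one offers ICM. Assumed: total N, Chatham share p, and the gap δ in 12-month event risk between Chatham and elsewhere.

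**1. Size of the chance imbalance.** With N/2 patients per arm, the SD of the between-arm difference in Chatham share is √(4p(1−p)/N). At p = 0.6, p(1−p) = 0.24.

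| | N = 240 | N = 120 |
|---|---|---|
| SD | √(0.96/240) = 0.0632 | √(0.96/120) = 0.0894 |
| 95% range (1.96 × SD) | ±12.4 points | ±17.5 points |
| Chance of a gap of 10 points or more | 11% | 26% |
| Shift in risk difference at that limit, δ = 20 points | 0.124 × 0.20 = 2.5 points | 0.175 × 0.20 = 3.5 points |
| Same, δ = 10 points | 1.2 points | 1.8 points |

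Simulating a single list in random blocks of 2 or 4 gave the same SDs as the formula to within Monte Carlo error (for example 0.101 against 0.100 at N = 100, p = 0.5). Over p = 0.3 to 0.7, a gap of 10 points or more occurred in about 32–37% of trials at N = 100 and 6–9% at N = 300.

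**2. Counts.** Take p = 0.5, a 10-point imbalance (55% against 45%) and no treatment effect. A county rate ratio of 1.5 gives an apparent rate ratio of (1 + 0.5 × 0.55)/(1 + 0.5 × 0.45) = 1.275/1.225 = 1.04. A county rate ratio of 2.0 gives 1.55/1.45 = 1.07.

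**3. Validity over all randomizations.** This was simulated with 3,000 trials per setting, p = 0.5, non-Chatham control risk 35%, and N = 100 or 240. The mean unadjusted estimate was within 0.2 points of the truth, and its type I error was 4.6–5.7% (Monte Carlo error √(0.05 × 0.95/3000) ≈ 0.4 points). Among trials that happened to have a gap of 10 points or more, type I error was about 5–8%, highest at δ = 30 points.

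**4. What adjustment buys.** The share of outcome variance due to county is p(1−p)δ²/0.24, where 0.24 is the outcome variance at an overall risk of 40% or 60%. At p = 0.6 this is 1% for δ = 10 points and 4% for δ = 20 points. Power for an assumed 15-point effect at N = 240, unadjusted against county-stratified Mantel-Haenszel:

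| County gap δ | Unadjusted | Stratified |
|---|---|---|
| 10 points | 70.0% | 70.3% |
| 20 points | 68.8% | 69.8% |
| 30 points | 66.4% | 69.6% |

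At N = 100 both stay at about 35–36%.

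**5. Mixed models.** A county term that is constant over time accounts for differences in level, which fall on the group main effect and not on the group-by-time slope. With N = 240, a 10-point imbalance and a 0.5-unit county difference, complete data gave the same group-by-time estimate with and without the term (difference below 1e-15; 30 simulated trials). With 60% missing at 12 months, the largest change was 0.0026 per month against a standard error of 0.013.

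**The case against.** The strongest reply is that unstratified blocked randomization is a sound design, and that chance imbalance in a baseline factor is part of the sampling error the standard error already covers. That stands. A reader might infer that the primary comparison is biased or that its error rate is inflated. The documents do not support this, and step 3 shows neither.

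Four further points also stand.

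- **Every quantity is assumed.** Nothing in the documents shows that risk differs by county or by facility. The power gain is visible only at a 30-point gap, and no calculation was made for referral facility.
- **For the binomial and Poisson models, the missing county term is read from silence.** No terms are listed for them at all. But silence leaves adjustment open to choice after results are seen, which is itself a reason to prespecify it.
- **A logit link changes the estimand.** The plan names no link. In 1,000 simulated trials (N = 240, p = 0.6, δ = 20 points), adjustment moved the mean log odds ratio from −0.447 to −0.466 and its standard error from 0.271 to 0.278. The ratio of estimate to standard error goes from 1.65 to 1.68 in size, so little changes except the meaning of the odds ratio.
- **Adding county to every mixed model would achieve almost nothing** for the group-by-time effect (step 5).

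What the reply does not answer is that a known baseline factor, which defines the comparator, goes unused when using it would need no new data.

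**Conclusion.** The point holds in a limited form. Allocation is not stratified, county determines the control service, and no county term is named in any model. A chance Chatham imbalance therefore stays uncorrected in the hospitalization and arrest estimates. Under the assumptions of a 60% share and a 20-point county risk gap, the shift is up to 2.5 points (N = 240) or 3.5 points (N = 120) at the 95% limit of imbalance, and the precision gained by adjusting is a few percent of outcome variance at most. If the true county gap is small, the effect is negligible.

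A reader might also infer that balancing or adjusting for county would settle the mixed CM/ICM comparator. It would not. A county main effect does not show whether the ODR effect differs between the CM counties and Chatham. That is a separate question, which needs within-area estimates or a county-by-group term.

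**What to change.** In Data Analyses:

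1. Add a Chatham versus other-county indicator as a prespecified baseline covariate in the binomial and Poisson models for hospitalizations and arrests. Add referral facility if numbers allow.
2. Make the adjusted estimate the reported one, with the unadjusted estimate alongside.
3. State the effect scale, for example a standardized risk difference, since an adjusted odds ratio is conditional.
4. In the mixed models, a county-by-time term is needed if adjustment is to affect the group-by-time estimate. A main effect alone is not worth adding for that purpose.
5. Tabulate county and referral facility by arm.

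Stratifying the list by Chatham versus the other counties applies only if allocation is not complete. With enrollment planned from December 2014 for about three years, and the document dated 2022 and revised 2024, it is probably too late. For the same reason, the amendment should state whether outcome data by arm had been seen when the covariate was chosen.

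The cost is a few sentences and no new data. The downsides are one or a few extra parameters, which matter most in the tests restricted to participants with non-zero values, and a conditional estimand if odds ratios are reported.

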### **Outcome Data Collection**

*Primary outcomes (hospitalizations and arrests).* Hospitalization data will be collected from three sources: the Georgia Department of Behavioral Health and Developmental Disabilities (DBHDD, the State's mental health agency), the CSU in Savannah, and the CSU in Brunswick. Because DBHDD operates all state psychiatric hospitals, they have complete admission and discharge data for the study timeframe. However, DBHDD only collected CSU data beginning in January 2017; as such, the two CSUs serving as referral sites will also provide admission and discharge data for the full study period.

Arrest data will be provided by the Georgia Crime Information Center (GCIC), within the Georgia Bureau of Investigation (the lead state law enforcement agency), in the form of the participants' record of arrests and prosecutions (RAP sheets). GCIC receives monthly arrest reports from >600 state and local law enforcement agencies; this information is stored in GCIC's crime database and is summarized in the RAP sheet. To test our arrest-related hypotheses, we will extract all arrests for the 12 months after enrollment. Arrest data will be available for all participants.

*Secondary outcomes (housing and recovery).* Data collection for the two secondary outcomes will be collected in-person, though retention is expected to be difficult based on the serious psychosocial impairment of the study sample and experience in the initial study. Two housing-related measures will be used. The *Housing Satisfaction Scale* (HSS) has 19 items covering choice, safety, privacy, and proximity. The *Housing Instability Index* (HII) is a sum of 10 items that ask participants about their housing situations over the past six months; the time frame was adapted to four months for this study to match the follow-up timepoints.

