To thoroughly assess recovery, we will examine five measures of constructs aligned with recent conceptualizations of recovery and the goals of ODR. First, the *Multnomah Community Ability Scale* (MCAS) is a 17-item instrument that measures social and community functioning, with documented good inter-rater and test-retest reliability, and validity. We added five items covering several areas deemed important for the study's purposes. Second, the *Maryland Assessment of Recovery in People with Serious Mental Illness* (MARS) is a 25-item instrument addressing recovery experiences, with documented excellent internal consistency and test-retest reliability, as well as construct validity and divergent validity. Third, the *Herth Hope Scale* (HHS) is a 30-item measure widely used to assess hope, and with well-documented psychometric properties. Fourth, the *Empowerment Scale* (ES) is a 28-item measure assessing self-esteem, perceived power, optimism/control over the future, and related constructs, with documented reliability and validity. Finally, the 21-item Community Navigation Scale was developed for the initial and current study—preliminary psychometric research suggests good internal consistency reliability and construct validity.

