### **Recovery Summary Score (RSS)**

Because the recovery measures are likely to be highly correlated, we will derive a summary measure to conserve power, which we call the overall Recovery Summary Score (RSS), using principal component analysis (PCA) with possible rotation, and then calculating a patient-specific summary measure by standardizing each of the five measures and then averaging for each subject and timepoint.

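### The assessor who opens the allocation envelope learns the arm, and nothing in the plan assigns the follow-up MCAS ratings to someone unaware of it

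*Combined protocol and SAP*

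**What the plan says.** All references are to the Combined protocol and SAP.

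- Referral, Assessment, and Randomization: "Trained research assessors will complete the initial/baseline assessment", about a week before discharge. Once eligibility, consent and the baseline ratings are done, "the research assessor will open the next envelope in the sequence and inform the ODR or CM provider of the treatment assignment".
- Under Outcome Data Collection, on housing and recovery: "Data collection for the two secondary outcomes will be collected in-person". The person who collects them at follow-up is not named.
- Outcome Data Collection, on the MCAS: a "17-item instrument that measures social and community functioning, with documented good inter-rater and test-retest reliability, and validity". Five study-specific items are added to it.
- Recovery Summary Score (RSS): the score is formed by "standardizing each of the five measures and then averaging for each subject and timepoint". The MCAS is one of the five.
- Data Analyses: linear mixed models with group, time and group-by-time terms, using "measures at baseline, 4-, 8-, and 12-months".

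The documents do not mention blinding or masking of raters anywhere. The opaque envelopes conceal the next assignment before it is made; they do not mask any rating made afterwards.

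**The concern.** The point is about how outcomes are measured, not about whether the next assignment can be guessed. Staff in the assessor role make the baseline ratings, and the procedure then tells one of them the arm. A site following the plan to the letter could have the same person randomize a participant and later score that participant's functioning in the knowledge of the arm.

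Participants cannot be masked to the kind of service they receive, so a rater-scored scale is where masking could still protect a secondary outcome. The timing makes this matter more. The envelope is opened after baseline, so that participant's baseline rating is made without knowledge of the arm, while the follow-up ratings may not be. Any rater expectation then appears as a difference in change between arms, which is the effect that the group-by-time term estimates. A spurious MCAS difference would also trigger the planned post-hoc comparison of ODR with intensive case management, which is run for measures showing a significant two-group difference.

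**Working it through.** The plan states no power, sample size, alpha or bias figure, so there is nothing to reproduce. The check has a textual part and an illustrative part.

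**Text.** Three questions were put to the documents.
1. Does the assessor learn the arm? Yes, by opening the envelope and notifying the provider.
2. Is that person kept away from later ratings? No section says so, and none names the follow-up rater.
3. Does the MCAS depend on a rater's judgement? This is inferred from the inter-rater reliability credited to it. The mode of administration is not stated.

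**How a rating bias enters the growth model.** Suppose ratings in one arm are shifted by b at 4, 8 and 12 months and by 0 at baseline. The times 0, 4, 8, 12 have mean 6, deviations −6, −2, 2, 6 and sum of squares 36 + 4 + 4 + 36 = 80. With balanced data the fitted slope difference is (−2 + 2 + 6)b/80 = 6b/80 = 0.075b per month, or 0.9b over 12 months. The planned model carries nearly all of the bias into the estimated effect.

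**Dilution in the RSS.** With five standardized measures, equal weights and a common correlation r, SD(RSS) = sqrt((1 + 4r)/5). A bias of b SD on the MCAS alone shifts the RSS by (b/5)/sqrt((1 + 4r)/5) in RSS SD units. For b = 0.3:
- r = 0.3: 0.06/sqrt(0.44) = 0.090
- r = 0.5: 0.06/sqrt(0.60) = 0.077
- r = 0.7: 0.06/sqrt(0.76) = 0.069

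**False-positive rates.** Assumptions: no true effect, two-sided alpha 0.05, n assessed per arm from 50 to 120, r from 0.3 to 0.7, bias on the MCAS only, and a single-timepoint normal test. For a standardized shift d, z = d/sqrt(2/n) and the rejection rate is Φ(z − 1.96) + Φ(−z − 1.96). Example: d = 0.3 and n = 100 give z = 0.3 × sqrt(50) = 2.12 and a rate of about 56%.

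| Assumed MCAS bias (SD) | MCAS false-positive rate | RSS shift (SD) | RSS false-positive rate | RSS rate at r = 0.7 only |
|---|---|---|---|---|
| 0.2 | 17% to 34% | 0.046 to 0.060 | 5.6% to 7.5% | 5.6% to 6.5% |
| 0.3 | 32% to 64% | 0.069 to 0.090 | 6.4% to 10.8% | 6.4% to 8.3% |
| 0.5 | 71% to 97% | 0.115 to 0.151 | 8.8% to 21.5% | 8.8% to 14.4% |

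The last column is shown because the plan expects the recovery measures to be highly correlated, which favours the upper end of the range for r.

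**The case against.** The strongest case on the other side has four parts.

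**The plan is silent; it does not prescribe unmasked rating.** A reader might infer that the same unmasked assessor is assigned to do the follow-up ratings. The documents do not say that. They name neither the follow-up rater nor the MCAS rater, and the inter-rater wording describes the published instrument rather than this trial's procedure. This stands, and it limits the claim. What remains is that one stated step unmasks a member of the assessing staff and no stated step undoes the consequence.

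**The reach is limited.** A reader might infer that the trial's main result is at risk. It is not, by this route: hospitalizations come from the state agency and the two crisis stabilization units, and arrests from the state crime records. This stands in full. The exposure is to one rater-scored measure and, diluted, to the summary built on it. It would be wider if an interviewer who knew the arm also influenced other in-person measures, but the documents give no basis for sizing that.

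**The rates are not this plan's error rates.** A reader might take a figure such as 56% as the plan's type I error for the MCAS. It comes from a single-timepoint test with an assumed bias and sample size, whereas the plan specifies a growth model. The rate under that model also depends on within-subject correlation and attrition, which are not given, and could be higher or lower. This stands: the figures show order of magnitude only.

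**Analysis is not powerless.** A reader might conclude that nothing can be done once ratings are made. That goes too far for the RSS: if the bias is confined to the MCAS, a summary of the other four measures is free of it. It does not repair the MCAS result itself.

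**Conclusion.** The concern holds as a gap in outcome measurement for a secondary endpoint, and it is worth correcting. Opening the envelope gives the assessor the arm, and nothing requires that someone unaware of it rates functioning at follow-up. The main exposure is the MCAS: under a constant follow-up shift, about nine-tenths of the bias reaches the 12-month change. For the RSS the effect is small at moderate bias, with a false-positive rate of about 6% to 11% for 0.2 to 0.3 SD, reaching about 22% only at 0.5 SD with 120 per arm and r = 0.3.

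The conclusion rests on one inference, that the MCAS is scored by a rater. The sizes rest on assumed values for bias, sample size and correlation, and on bias confined to the MCAS. The documents support neither a finding that unmasked rating will occur nor any doubt about the primary outcomes on this ground.

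**What to change.** **If follow-up is still running**
- Have a research staff member who makes no outcome ratings, and who is independent of the ODR and CM providers, open the envelope and notify the provider; the study coordinator or the statistician's office are examples. Provider-side staff should not take this on: with blocks of 2 or 4, that would create a concealment risk.
- Failing that, have each participant's follow-up MCAS done by a different existing assessor who has not been told the arm. The plan refers to assessors in the plural but does not show that a second one is available at every site, so this needs confirming.
- Record at each visit whether the rater knew the arm, for description only. Restricting the analysis to visits with unaware raters would condition on an event after randomization that may differ by arm; ODR clients, for example, are to have at least weekly contact with the team.

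**In either case**
- Add a sensitivity analysis of the RSS formed from the four measures other than the MCAS. It omits the functioning component, so it supplements the planned score and does not replace it.

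**If follow-up is complete**
- Enrollment was planned from December 2014 for about three years, with 12 months of follow-up, which points to about the end of 2018. The document is dated 2022 and was revised in 2024, so the procedural change may come too late. In that event, report who made the ratings and whether they knew the arm, and interpret the MCAS result accordingly.

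**Cost.** A few sentences of procedure, one extra data field, one extra model run and some scheduling effort. Masking will be imperfect because participants may reveal their arm.
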